5.2.2. Analyses for Continuous Endpoints

For continuous endpoints, (eg, change from baseline in SARS-CoV-2 RNA level in NP swabs and in plasma over time), results and/or changes from baseline over time, as applicable will be summarized with descriptive statistics (mean, SD, etc).

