5.3. Methods to Manage Missing Data

For SARS-CoV-2 RNA data, samples producing a result of <LLOQ or undetectable will not be considered missing, but rather will be imputed using values of 1.7 [log₁₀(50)] or 0.0 log₁₀ copies/mL, respectively. Missing SARS-CoV-2 RNA data will not be imputed.

As all analyses are descriptive, missing endpoint data will result in a summary where the N for that endpoint (and time point) is smaller than the total N of the corresponding analysis set. No imputation of the missing data will be performed.

For safety data, missing and partial dates will be programmatically handled according to Pfizer standards.

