6.1.1. Main Analysis

The primary descriptive analysis will summarize, separately for the main study population and the population with rebound, the number and proportion of participants with sustained NP swab SARS-CoV-2 RNA <LLOQ (defined as <2.0 log₁₀ copies/mL) from Day 15 through Day 44 for each treatment arm in the Evaluable Analysis Set and FAS. Participants DMB02-GSOP-RF02 7.0 *Statistical Analysis Plan Template* 31-Jan-2022

> PFIZER CONFIDENTIAL TMF Doc ID: 98.03 Page 16 of 32

receiving non-study antiviral or monoclonal antibody therapy post-baseline (between randomization and Day 44 visit) for the treatment of COVID-19 will be considered as not achieving sustained NP swab SARS-CoV-2 RNA <LLOQ in the primary analysis.

As viral load measurements from NP swabs are taken on Days 15, 21, 28, 35, and 44 during the time interval from Day 15 to Day 44, all of the measurements that are non-missing must be <LLOQ (including undetectable), and the Day 15, Day 44, and no more than one of the Day 21, 28, and 35 measurements can be missing in order for the event to be considered sustained.

In addition, 95% CIs for the proportion of participants with sustained NP swab SARS-CoV-2 RNA <LLOQ from Day 15 through Day 44 for each treatment arm will be calculated using binomial distribution normal approximation. The difference in proportions for the primary endpoint and associated 95% CI will be calculated for each pairwise comparison of the treatment arms.

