The Day 35 visit is the last possible day the sustained NP swab SARS-CoV-2 RNA<LLOQ can be achieved.

DMB02-GSOP-RF02 7.0 Statistical Analysis Plan Template 31-Jan-2022 PFIZER CONFIDENTIAL TMF Doc ID: 98.03 Page 18 of 32 The time to the sustained event is defined as:

- For a participant with sustained event at Day *t*, the First Event Date is the date of the Day *t* measurement, and time to event will be calculated as (First Event Date) (First Dose Date) +1.
- For a participant for which no possible value of *t* ≤ the 35 visit satisfies the criteria for a sustained event (censored), censoring date will be the date of the last available protocol-specified SARS-CoV-2 RNA measurement other than Day 44, and time will be calculated as (Censoring Date) (First Dose Date) +1.

Time to sustained NP swab SARS-CoV-2 RNA<LLOQ will be summarized graphically using Kaplan-Meier plots for each of the treatment groups in main study population.

6.2.3. Proportion of participants with SARS-CoV-2 RNA <LLOQ in plasma over time.

• The proportion of participants with SARS-CoV-2 RNA <LLOQ as measured in plasma will be summarized at each study visit through week 24 for each treatment arm. In addition, 95% CIs for the proportion of participants with SARS-CoV-2 RNA <LLOQ in plasma at each study visit will be calculated for each treatment arm.

6.2.4. Proportion of participants with SARS-CoV-2 RNA level in NP swabs <2.0 log₁₀ copies/mL at each study visit

The proportion of participants with SARS-CoV-2 RNA < 2.0 log₁₀ copies/mL as measured by NP swab will be summarized at each study visit through Week 24 for each treatment arm. In addition, 95% CIs for the proportion of participants with SARS-CoV-2 RNA <2.0 log₁₀ copies/mL as measured by NP swabs at each study visit will be calculated for each treatment arm.

6.2.5. Change from baseline in SARSCoV-2 RNA level in NP swabs and in plasma over time.

Descriptive statistics by treatment group for the change from baseline to each study visit (Day 5, 10, 15, 21, 28, 35, 44) will be provided. Participants are excluded from the analysis for reasons of Not Detected, Zero or Missing baseline and/or post-baseline viral load results.

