6.2.6. Rebound in SARS-CoV-2 RNA level in NP swabs

Rebound in SARS-CoV-2 RNA level in NP swabs at follow up (ie, any study visit after end of active treatment through Day 44) that is defined as a half (0.5) \log_{10} copies/mL increase or greater in SARS-CoV-2 RNA level relative to end of active treatment SARS-CoV-2 RNA level based on treatment regimen, with a follow-up viral RNA level \geq 2.5 \log_{10} copies/mL.

In addition, two alternative definitions of rebound will also be evaluated:

• Rebound that is defined as: SARS-CoV-2 RNA level in NP swabs at follow up (ie, any study visit after end of active treatment through Day 44) that is defined as a half (0.5) log₁₀ copies/mL increase or greater in SARS-CoV-2 RNA level

DMB02-GSOP-RF02 7.0 Statistical Analysis Plan Template 31-Jan-2022 PFIZER CONFIDENTIAL TMF Doc ID: 98.03 Page 19 of 32 relative to end of active treatment SARS-CoV-2 RNA level based on treatment regimen, with a follow-up viral RNA level \geq **3.0** log₁₀ copies/mL.

• Rebound that is defined as: SARS-CoV-2 RNA level in NP swabs at follow up (ie, any study visit after end of active treatment through **Day 28**) that is defined as a half (0.5) log₁₀ copies/mL increase or greater in SARS-CoV-2 RNA level relative to end of active treatment SARS-CoV-2 RNA level based on treatment regimen, with a follow-up viral RNA level ≥3.0 log₁₀ copies/mL.

The rebound analyses will be restricted to those participants with non-missing end of active treatment SARS-CoV-2 RNA measurement and at least one non-missing measurement among the study visits after end of treatment through the Day 44 visit (or through the Day 28 visit for the second alternative definition of rebound analysis).

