Appendix 1. Summary of Efficacy Analyses

DMB02-GSOP-RF02 7.0 Statistical Analysis Plan Template 31-Jan-2022 PFIZER CONFIDENTIAL TMF Doc ID: 98.03 Page 26 of 32

Endpoint	Analysis Type	Population	Data Inclusion and Rules for Handling Intercurrent Events and Missing Data	Analysis Model
			No imputation of missing data	normal approximation
Proportion with sustained SARS- CoV-2 RNA < LLOQ from Day 15 to Day 44 (NP)	Supplementary	Evaluable	Participants who do not meet the protocol-defined immunocompromised criteria will be excluded. Intercurrent event: non-study anti- viral or mAb therapy – participant considered failure No imputation of missing data	Descriptive (n, %), 95% CI for proportion and the difference in proportion using binomial distribution normal approximation
Time to first SARS- CoV-2 RNA < LLOQ (NP)	Secondary	Evaluable with BL ≥ LLOQ	No imputation for missing data	KM curves
Time to sustained SARS-CoV-2 RNA < LLOQ (NP)	Secondary	Evaluable with BL ≥ LLOQ	No imputation for missing data	KM curves
Proportion with SARS-CoV-2 RNA <lloq over="" time
(plasma)</lloq>	Secondary	Evaluable	Missing at timepoint imputed as not <lloq< td="">Descriptive (n, %)	</lloq<>	Descriptive (n, %)
Proportion with SARS-CoV-2 RNA <lloq over="" time
(NP)</lloq>	Secondary	Evaluable	Missing at timepoint imputed as not <lloq< td="">Descriptive (n, %)	</lloq<>	Descriptive (n, %)
Change from baseline in SARS- CoV-2 RNA level over time (NP & plasma)	Secondary	Evaluable	<lloq 1.7,="" as="" imputed="" post-bl
undetectable imputed as 0.0, no imputation for missing data</lloq>	Descriptive summary
Rebound in SARS- CoV-2 RNA up to Day 44 (NP) defined as a half log_{10} copies/mL increase or greater relative to EOT (active) with follow-up viral RNA level $\geq 2.5 \ log_{10}$ copies/mL	Secondary	Evaluable with EOT (active) and 1 post-EOT not missing	No imputation for missing data	Descriptive (n, %)

DMB02-GSOP-RF02 7.0 Statistical Analysis Plan Template 31-Jan-2022 PFIZER CONFIDENTIAL TMF Doc ID: 98.03 Page 27 of 32

Endpoint	Analysis Type	Population	Data Inclusion and Rules for Handling Intercurrent Events and Missing Data	Analysis Model
Rebound in SARS- CoV-2 RNA up to Day 44 (NP) defined as a half log_{10} copies/mL increase or greater relative to EOT (active) with follow-up viral RNA level \geq 3.0 log_{10} copies/mL	Secondary	Evaluable with EOT (active) and 1 post-EOT not missing	No imputation for missing data	Descriptive (n, %)

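### SAP 6.2.5 excludes post-baseline undetectable viral RNA results from change from baseline, while Appendix 1 and SAP 5.3 keep them at 0.0 log10, and no precedence is stated (minor)

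*SAP*

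**What the plan says.** Three places in the SAP bear on how an undetectable result enters this endpoint.

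- **SAP 6.2.5** plans "Descriptive statistics by treatment group for the change from baseline to each study visit" (Days 5 to 44) and then adds: "Participants are excluded from the analysis for reasons of Not Detected, Zero or Missing baseline and/or post-baseline viral load results".
- **SAP Appendix 1**, in the row for the same endpoint (NP and plasma), sets results below the LLOQ to 1.7 and has post-baseline "undetectable imputed as 0.0, no imputation for missing data".
- **SAP 5.3**, the general rule for viral RNA, says that "samples producing a result of <LLOQ or undetectable will not be considered missing, but rather will be imputed", at 1.7 for below LLOQ and 0.0 for undetectable. Missing results are not imputed.

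SAP 5.2.2 says of continuous endpoints that results and/or "changes from baseline over time, as applicable will be summarized with descriptive statistics (mean, SD, etc"). SAP 2.1 lists no modification of the protocol's analysis plan. The version history does not mention this rule. Protocol 9.3 leaves the handling of missing data to the SAP. Nothing says which text governs.

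**The concern.** A programmer working from 6.2.5 would drop every post-baseline undetectable result. A programmer working from Appendix 1 would keep each one at 0.0. Their tables would show different Ns and different means at every visit with an undetectable result.

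The 6.2.5 rule is also the weaker summary on its merits. Undetectable RNA after baseline is the outcome that treatment is meant to produce. Removing those results leaves a mean over participants who still have detectable virus. If the arms clear at different rates, each arm's mean rests on a differently selected subset, and a reader who sets the three columns side by side is no longer comparing randomised groups.

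**Working it through.** **1. The plan's own figure.** SAP 5.3 gives the below-LLOQ value as 1.7 = log10(50). log10(50) = 1.699, so it reproduces.

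**2. The rules side by side.**

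| Result | SAP 6.2.5 | Appendix 1 row | SAP 5.3 |
|---|---|---|---|
| Post-baseline, detected below LLOQ | not excluded | 1.7 | 1.7 |
| Post-baseline, undetectable | **excluded** | **0.0** | **0.0** |
| Missing | excluded | not imputed | not imputed |
| Baseline undetectable | excluded | its 0.0 rule covers post-baseline only | 0.0 |

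The conflict is confined to undetectable results. Imputing first and applying 6.2.5 afterwards does not resolve it, because 6.2.5 also excludes zeros, which is the value just imputed.

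**3. Size of the gap in a visit mean.** Let p be the fraction undetectable at the visit, Bu their mean baseline, |D| the mean decline among those detectable, and s the substituted value.

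- Undetectables included: p(s − Bu) + (1 − p)(−|D|)
- Undetectables excluded: −|D|
- Excluded minus included: p(Bu − s − |D|)

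The documents give no viral-load distribution, so the inputs are assumptions: |D| = 3.5, Bu = 5 to 6. A positive gap means that 6.2.5 shows the smaller decline.

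| s | p = 20% | p = 50% |
|---|---|---|
| 0.0 (SAP value) | 0.30 to 0.50 | 0.75 to 1.25 |
| 1.0 | 0.10 to 0.30 | 0.25 to 0.75 |
| 1.7 | −0.04 to 0.16 | −0.10 to 0.40 |

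For example, at p = 20%, Bu = 5 and s = 0.0: 0.20 × (5 − 0.0 − 3.5) = 0.30.

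**4. Two arms.** Take two arms of 50 (the planned size), an assumed 30% and 60% undetectable, the same baseline, and the same mean d among detected results.

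- At s = 0.0 the visit means are 0.7d and 0.4d. The difference is 0.3d, which is 0.60 to 0.90 log10 for d = 2.0 to 3.0.
- With exclusion the difference is 0.00, on n = 35 and n = 20.

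This case is deliberately simple, since all of the arm difference lies in the undetectable fraction.

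**5. A less stylised check by simulation.** All inputs are assumed: baseline normal with mean 6 and SD 1.5, values below 2 dropped; decline SD 1.8; mean declines 3 v 4, 3.5 v 4.5 and 4 v 5; detection cut-offs 0.5, 1.0 and 1.5; detected values below 2.0 set to 1.7; 1,000,000 per arm. Between 14% and 58% were undetectable.

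| s | Gap in mean decline | Effect of exclusion on the arm difference |
|---|---|---|
| 0.0 | 0.28 to 0.98 | toward zero by 0.10 to 0.21 |
| 0.5 | 0.21 to 0.68 | toward zero by 0.03 to 0.13 |
| 1.0 | 0.10 to 0.43 | at most 0.06 either way |
| 1.7 | −0.19 to 0.20 | wider by 0.05 to 0.17 |

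No arm difference changed sign. A re-run with a different seed gave the same ranges to within about 0.01. Plasma was not modelled.

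**The case against.** **A reconciling reading exists.** Appendix 1 limits its 0.0 rule to post-baseline results. If 6.2.5 means not detected or zero at baseline, and missing at either time, the texts agree. This may be what was intended. But the three reasons in 6.2.5 share one closing phrase that covers baseline and post-baseline alike, and nothing signals a split. Even on this reading the sentence needs rewording.

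**6.2.5 might be the intended rule.** A reader might infer that change from baseline is the only summary in which 0.0 matters, so that Appendix 1 must be what the sponsor meant. The documents do not support that. SAP 5.2.2 also allows summaries of results over time, where 0.0 would count. Nor is Appendix 1 a safe guide to intent, because it departs from the body elsewhere. It imputes missing visit results as not below LLOQ, against the no-imputation rule in 5.3. It also caps hospitalisation, ICU and ventilation/ECMO at Day 44, where 6.2.11 to 6.2.13 also plan Week 24. Intent is therefore open.

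**The 0.0 value is itself arbitrary, and the harm is conditional.** This stands. With s = 1.7 the gap can vanish or change sign. The figures also assume exclusion visit by visit, whereas 6.2.5 could be read as removing the participant from the whole analysis.

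**Little depends on it.** This also stands. SAP 5.1 plans no hypothesis test, and 6.2.5 plans by-arm summaries only. The primary endpoint keeps undetectable results: "all of the measurements that are non-missing must be <LLOQ (including undetectable"). Clearance is reported separately as times in 6.2.1 and 6.2.2, and in 6.2.4 as a proportion "as measured by NP swab will be summarized at each study visit through Week 24 for each treatment arm", so cleared participants are not hidden from the reader.

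**Conclusion.** The inconsistency holds on the ordinary wording and needs no numerical assumption. For post-baseline undetectable results, 6.2.5 says exclude, Appendix 1 and 5.3 say include at 0.0, and no precedence is given. Applied by visit as worded, 6.2.5 summarises a subset chosen by the post-randomisation outcome.

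The size is illustrative. With the SAP's 0.0 and the assumed inputs above, the mean decline differs by roughly 0.3 to 1.25 log10 for 20% to 50% undetectable. Both size and direction depend on the substituted value and on the unknown viral-load distribution. The gap is zero if no result is undetectable.

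A reader might go further and conclude that the comparison of treatment durations is biased in a known direction. The documents do not support this: no formal comparison is planned on this endpoint, the direction is not fixed, and no simulated arm difference reversed. Severity: minor.

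**What to change.** Reconcile 6.2.5 with 5.3 and Appendix 1. Possible text for 6.2.5:

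*Participants with a missing or undetectable baseline are excluded. At each post-baseline visit, participants with a missing result at that visit are excluded from that visit's summary; post-baseline below-LLOQ and undetectable results are included at 1.7 and 0.0 log10 copies/mL.*

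The baseline sentence is needed. SAP 3.4 provides for baselines classed as missing, from which no change can be computed, and for undetectable baselines, which under 5.3 would otherwise enter at 0.0. State the same exclusion in the Appendix 1 row, and print N and the number undetectable beside each mean. One sensitivity summary with another substituted value, for example 1.7, is optional.

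The cost is one or two SAP sentences, one Appendix 1 cell and a small programming change, with no new data. The downside is that the mean then depends on the substituted value, which the printed count of undetectable results makes visible.

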6.2.6. Rebound in SARS-CoV-2 RNA level in NP swabs

Rebound in SARS-CoV-2 RNA level in NP swabs at follow up (ie, any study visit after end of active treatment through Day 44) that is defined as a half (0.5) \log_{10} copies/mL increase or greater in SARS-CoV-2 RNA level relative to end of active treatment SARS-CoV-2 RNA level based on treatment regimen, with a follow-up viral RNA level \geq 2.5 \log_{10} copies/mL.

In addition, two alternative definitions of rebound will also be evaluated:

• Rebound that is defined as: SARS-CoV-2 RNA level in NP swabs at follow up (ie, any study visit after end of active treatment through Day 44) that is defined as a half (0.5) log₁₀ copies/mL increase or greater in SARS-CoV-2 RNA level

DMB02-GSOP-RF02 7.0 Statistical Analysis Plan Template 31-Jan-2022 PFIZER CONFIDENTIAL TMF Doc ID: 98.03 Page 19 of 32 relative to end of active treatment SARS-CoV-2 RNA level based on treatment regimen, with a follow-up viral RNA level \geq **3.0** log₁₀ copies/mL.

• Rebound that is defined as: SARS-CoV-2 RNA level in NP swabs at follow up (ie, any study visit after end of active treatment through **Day 28**) that is defined as a half (0.5) log₁₀ copies/mL increase or greater in SARS-CoV-2 RNA level relative to end of active treatment SARS-CoV-2 RNA level based on treatment regimen, with a follow-up viral RNA level ≥3.0 log₁₀ copies/mL.

The rebound analyses will be restricted to those participants with non-missing end of active treatment SARS-CoV-2 RNA measurement and at least one non-missing measurement among the study visits after end of treatment through the Day 44 visit (or through the Day 28 visit for the second alternative definition of rebound analysis).

6.2.7. Incidence of TEAEs

• The incidence of TEAEs will be summarized by treatment group, by SOC and PT using the Safety Analysis Set.

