**Study Arms and Duration:**

Eligible participants for this study will be randomly assigned (1:1:1) to receive nirmatrelvir plus ritonavir orally q12h as specified in the table below.

Study Intervention(s)				
Intervention Name	Nirmatrelvir	Placebo for nirmatrelvir	Ritonavir	Placebo for ritonavir
Arm Name (group of participants receiving a specific treatment or no treatment)	nirmatrelvir/ritonavir	placebo	nirmatrelvir/ritonavir	placebo
Unit Dose Strength(s)	150 mg	0 mg	100 mg	0 mg
Route of Administration	Oral	Oral	Oral	Oral
Use	Experimental	Placebo	Experimental	Placebo
IMP or NIMP/AxMP	IMP	IMP	IMP	IMP

Study Arm(s)			
Arm Title	Nirmatrelvir/ritonavir 5-day	Nirmatrelvir/ritonavir 10-day	Nirmatrelvir/ritonavir 15-day
Arm Type	Experimental, placebo	Experimental, placebo	Experimental
Arm Description	Participants will receive nirmatrelvir/ritonavir 300 mg/100 mg (or 150 mg/100 mg for participants with eGFR $\geq$ 30 to <60 mL/min/1.73 m  or eCrCl $\geq$ 30 to <60 mL/min) q12h from Day 1 through Day 5 followed by placebo for nirmatrelvir/placebo for ritonavir q12h for Day 6 through Day 15.	Participants will receive nirmatrelvir/ritonavir 300 mg/100 mg (or 150 mg/100 mg for participants with eGFR $\geq$ 30 to <60 mL/min/1.73 m  or eCrCl $\geq$ 30 to <60 mL/min) q12h from Day 1 through Day 10 followed by placebo for nirmatrelvir/placebo for ritonavir q12h for Day 11 through Day 15.	Participants will receive nirmatrelvir/ritonavir 300 mg/100 mg (or 150 mg/100 mg for participants with eGFR $\geq$ 30 to <60 mL/min/1.73 m  or eCrCl $\geq$ 30 to <60 mL/min) q12h from Day 1 through Day 15.

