Arm Title	Nirmatrelvir/ritonavir 5-day	Nirmatrelvir/ritonavir 10-day	Nirmatrelvir/ritonavir 15-day
Arm Type	Experimental, placebo	Experimental, placebo	Experimental
Arm Description	Participants will receive nirmatrelvir/ritonavir 300 mg/100 mg (or 150 mg/100 mg for participants with eGFR $\geq 30$ to $< 60$ mL/min/1.73 m  or eCrCl $\geq 30$ to $< 60$ mL/min) q12h from Day 1 through Day 5 followed by placebo for nirmatrelvir/placebo for ritonavir q12h for Day 6 through Day 15.	Participants will receive nirmatrelvir/ritonavir 300 mg/100 mg (or 150 mg/100 mg for participants with eGFR $\geq 30$ to $< 60$ mL/min/1.73 m  or eCrCl $\geq 30$ to $< 60$ mL/min) q12h from Day 1 through Day 10 followed by placebo for nirmatrelvir/placebo for ritonavir q12h for Day 11 through Day 15.	Participants will receive nirmatrelvir/ritonavir 300 mg/100 mg (or 150 mg/100 mg for participants with eGFR $\geq 30$ to $< 60$ mL/min/1.73 m  or eCrCl $\geq 30$ to $< 60$ mL/min) q12h from Day 1 through Day 15.
Associated Intervention Labels	Nirmatrelvir/ritonavir (5-day)	Nirmatrelvir/ritonavir (10-day)	Nirmatrelvir/ritonavir (15-day)

Nirmatrelvir/ritonavir may be shipped by courier to study participants if permitted by local regulations and in accordance with storage and transportation requirements for the nirmatrelvir/ritonavir. Pfizer does not permit the shipment of nirmatrelvir/ritonavir by mail. The tracking record of shipments, including temperature monitoring data, and the chain of custody of nirmatrelvir/ritonavir must be kept in the participant's source documents/medical records.

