#### **8.4.1. Time Period and Frequency for Collecting AE and SAE Information**

The time period for actively eliciting and collecting AEs and SAEs (“active collection period”) for each participant begins from the time the participant provides informed consent, which is obtained before undergoing any study-related procedure and/or receiving study intervention, through and including a minimum of 28 calendar days, except as indicated below, after the last administration of the study intervention.

Follow-up by the investigator continues throughout the active collection period and until the AE or SAE or its sequelae resolve or stabilize at a level acceptable to the investigator.

When a clinically important AE remains ongoing at the end of the active collection period, follow-up by the investigator continues until the AE or SAE or its sequelae resolve or stabilize at a level acceptable to the investigator and Pfizer concurs with that assessment.

For participants who are screen failures, the active collection period ends when screen failure status is determined.

If the participant withdraws from the study and also withdraws consent for the collection of future information, the active collection period ends when consent is withdrawn.

If a participant permanently discontinues or temporarily discontinues study intervention because of an AE or SAE, the AE or SAE must be recorded on the CRF and the SAE reported using the PSSA.

After the defined active collection period for safety events, long-term follow-up visits are also conducted at Weeks 12 and 24. Any new SAE occurring during this long-term follow-up period and determined to be related to study intervention must be reported to Pfizer Safety immediately upon awareness and under no circumstance should this exceed 24 hours.

Investigators are not obligated to actively seek information on AEs or SAEs after the participant has concluded study participation. However, if the investigator learns of any SAE,

including a death, at any time after a participant has completed the study, and they consider the event to be reasonably related to the study intervention, the investigator must promptly report the SAE to Pfizer using the PSSA.

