3.5.1. Adverse Events

An adverse event (AE) is any untoward medical occurrence in a study participant administered a product or medical device; the event need not necessarily have a causal relationship with the treatment or usage. An adverse event is considered a Treatment-Emergent Adverse Event (TEAE) if the event started on or after the study medication start date. Since time of AE is not collected, AEs that begin on day 1, even if prior to study treatment start, will be considered TEAE.

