4. ANALYSIS SETS (POPULATIONS FOR ANALYSIS)

Data for all participants will be assessed to determine if participants meet the criteria for inclusion in each analysis population prior to unblinding and releasing the database and classifications will be documented per standard operating procedures.

For purposes of analysis, the following analysis sets are defined (excluding participants from Site 1001 from all efficacy analyses):

Participant Analysis Set	Description
Full analysis set (FAS)	All participants randomly assigned to study intervention.
Evaluable analysis set/Safety Analysis Set (SAS)	All participants randomly assigned to study intervention and who take at least 1 dose of study intervention.

The evaluable analysis set will be the primary analysis set for evaluating the primary estimand.

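### Adverse events are tabulated only as cumulative incidence by arm, which attenuates the contrast due to the added 5 or 10 days of drug; tables by onset period would sharpen it cheaply

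*SAP*

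**What the plan says.** **Tables.** SAP 6.2.7: "The incidence of TEAEs will be summarized by treatment group, by SOC and PT using the Safety Analysis Set". SAP 6.2.8 treats SAEs and AEs leading to discontinuation the same way, and SAP 6.5.1 says no more for coded AEs in general. None of these sections mentions time of onset. SAP 6.5 otherwise relies on the sponsor's standard tables and listings.

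**What counts.** Under SAP 3.5.1 an event is treatment-emergent "if the event started on or after the study medication start date", with no end date given. Because clock time is not recorded for AEs, "AEs that begin on day 1, even if prior to study treatment start, will be considered TEAE". Protocol 8.4.1 collects events "through and including a minimum of 28 calendar days, except as indicated below, after the last administration of the study intervention". That last dose may be active or placebo and falls on Day 15 or 16, so collection reaches at least Day 43 (15 + 28) or Day 44 (16 + 28) in every arm. The safety set is "All participants randomly assigned to study intervention and who take at least 1 dose of study intervention".

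**Exposure.** In the Protocol synopsis (Study Arms and Duration) and Protocol 6.1, the arms receive active drug as follows:
- 5-day arm: "q12h from Day 1 through Day 5 followed by placebo for nirmatrelvir/placebo for ritonavir q12h for Day 6 through Day 15"
- 10-day arm: "q12h from Day 1 through Day 10 followed by placebo for nirmatrelvir/placebo for ritonavir q12h for Day 11 through Day 15"
- 15-day arm: "q12h from Day 1 through Day 15"

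Protocol 6.1.1 sets 30 doses in total, two a day. The first 10 doses are therefore the same drug in all three arms, and the first 20 are the same in the 10- and 15-day arms.

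**The concern.** The trial asks whether a longer course is worth giving, and safety and tolerability are a stated secondary objective. What a longer course adds is doses 11 to 20 or 11 to 30. After dose 10 the 5-day arm is a blinded, randomised placebo control for those doses, and after dose 20 the 10-day arm becomes one for the 15-day arm. No planned AE table makes use of this.

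Instead, each AE row mixes events from the common period, which can differ between arms only by chance, with events that the added exposure could cause. Three things are lost:

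- A participant whose event starts early already counts in that row, so a later event of the same kind adds nothing.
- An event that starts on Day 2 and lasts as long as drug is taken counts the same at 5 days as at 15 days. Change in taste, which the Protocol synopsis lists among the common events, could behave this way.
- A participant in the 5-day arm who stops on Day 8 is stopping placebo, but appears in the same discontinuation row as someone stopping active drug.

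The data to support Days 11 to 15 are also thinner: the healthy-participant safety data cited in Protocol 4.3 go up to 10 days of dosing.

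**Working it through.** **1. The plan's own figures.** The documents give no TEAE figure. The only precision figure for 50 per arm is Table 2 (SAP 2.4, primary endpoint). Its entry at p = 0.5 is 0.139, and 1.96 × √(0.5 × 0.5/50) = 0.1386, so the figure reproduces, though as a half-width. The same n and normal approximation are used below.

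**2. Inputs.** From the documents: about 50 per arm in the main population (SAP 2.4), and common exposure for the first 10 doses (Protocol 6.1). Assumed, because no rates by day are given:
- e, the risk of an event with onset in the common period, is 40% in every arm;
- w, the risk in the added-exposure window (doses 11 to 30), is 10% on placebo (5-day arm) and 20% on active drug (15-day arm);
- l, the risk from then to the end of collection, is 5%.

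The three periods are taken as independent. Each participant counts once per row, which is the usual meaning of incidence although the SAP does not say so.

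**3. Formula.** Cumulative incidence = 1 − (1 − e)(1 − w)(1 − l). The difference between arms is therefore (1 − e) times the difference in onset risk from dose 11 onward.

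**4. Results, 5-day v 15-day.** SE = √(p₁q₁/50 + p₂q₂/50).

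| Count | 5-day | 15-day | Difference | SE | Difference/SE |
|---|---|---|---|---|---|
| Cumulative from first dose | 1 − 0.6 × 0.9 × 0.95 = 48.7% | 1 − 0.6 × 0.8 × 0.95 = 54.4% | 5.7 points | 9.98 | 0.57 |
| Doses 11 to 30 only | 10% | 20% | 10 points | 7.07 | 1.41 |
| Dose 11 to end of collection | 1 − 0.9 × 0.95 = 14.5% | 1 − 0.8 × 0.95 = 24.0% | 9.5 points | 7.83 | 1.21 |

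The shrinkage factor checks: 0.6 × 9.5 = 5.7.

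**5. Range of early incidence.** At e = 20% the cumulative difference is 0.8 × 9.5 = 7.6 points (0.80 SE). At e = 50% it is 0.5 × 9.5 = 4.75 points (0.48 SE).

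**6. A second set of rates.** Assume onset after the common doses of 10% v 25%. The difference from that point is 15.0 points with a 95% half-width of 14.6. With e = 40%, the cumulative figures are 46% v 55%: 9.0 points with a half-width of 19.5.

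**7. Dependence.** If people with early events are also prone to later ones, the loss is greater. With a shared logistic-normal frailty of SD 1, 2 or 3, the 9.0 points of step 6 become 7.4, 5.3 or 3.7.

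**8. Terms that are rare early.** With e = 5%, w = 2% v 8% and l = 1%, the cumulative difference is 0.95 × 6 × 0.99 = 5.6 points, against 6.0 in the window. The size is nearly intact, although the standardised difference still falls from 1.39 to 0.92.

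**9. Cutting the window further.** Spread 10% v 20% evenly over two halves: 1 − √0.9 = 5.1% and 1 − √0.8 = 10.6% in each. Doses 11 to 20 (5-day v the other two arms, 50 v 100) give 1.24 SE; doses 21 to 30 (5-day v 15-day, 50 v 50) give 1.01 SE. Neither reaches 1.41, so one contrast should be named as the main one.

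**The case against.** A reader might infer more than the documents support, in four ways.

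- *That the cumulative table is invalid, or that harm from Days 6 to 15 is the only safety question the randomisation can answer.* Neither follows. Incidence by arm from first dose is a fair randomised comparison of whole regimens and fits the descriptive objective. Harm from longer exposure may also begin after Day 15, so a window closing there would itself be too narrow.
- *That no safety analysis uses the placebo period.* Laboratory values are summarised over time by arm (SAP 6.5.2). SAP 6.2.16 and 6.2.17 give duration and severity over time for targeted symptoms, with severe symptoms split at the end of active treatment. Protocol Appendix 10 includes diarrhoea, vomiting, headache and loss of taste, which overlap the expected AEs. Some persistence will therefore be visible, though mixed with disease symptoms and not recorded as AEs.
- *That every row is badly diluted.* SAP 6.2.7 reports by SOC and PT, and many preferred terms will be rare early, as in step 8. The heavy dilution applies to the any-TEAE row and common terms, and its size rests on assumed rates.
- *That calendar-day periods would do.* The schedule of activities lets dosing end on Day 16 if only one dose is taken on Day 1, so a 5-day active course can run into Day 6. AE clock time is not available to place boundary-day events.

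It can also be said that the trial is descriptive, that SAP 6.5.1 calls safety analysis generally exploratory, that an external committee reviews unblinded safety data, and that the sponsor's standard outputs cannot be seen. These points lower the urgency. They do not supply the missing comparison in the planned tables.

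**Conclusion.** The point holds as a loss of sensitivity. TEAEs, SAEs and AEs leading to discontinuation have no summary by onset period, so the contrast due to the added doses is reported in attenuated form. Under independence the attenuation factor is (1 − early incidence). For an any-TEAE row with an assumed 40% early incidence, a 10-point excess in the added-exposure window appears as 5.7 points, and the standardised difference drops from 1.41 to 0.57. For terms that are rare early the difference is almost unchanged.

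The gain from the remedy should not be oversold. Carrying the window on to the end of collection, as is right for delayed harm, gives 9.5 points and 1.21 SE. Its 95% half-width is 1.96 × 7.83 = 15.3 points, so the interval would still include zero. This is a cheap improvement to a descriptive safety analysis; the existing tables need no correction.

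**What to change.** Keep the cumulative tables. In SAP 6.2.7, 6.2.8 and 6.5.1 add:

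1. **Onset-period tables** of new or worsened TEAEs, SAEs and AEs leading to discontinuation, by arm. Use scheduled doses 1–10, 11–20 and 21–30, then to the end of AE collection. Take the limits from each participant's dosing record (the electronic dosing diary in Protocol 6.5) rather than calendar days, and apply the same dose-number limits in every arm. Give a rule for events starting on a boundary day, and one for what counts as worsened.
2. **Main contrasts**, with risk differences and 95% CIs: 5-day v 15-day, and 5-day v 10-day, for onset after dose 10 through the end of collection; 10-day v 15-day for onset after dose 20.
3. **Persistence**: for TEAEs that start in the common period, duration and whether still ongoing at the end of the 10- and 15-day courses, by arm.

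Treatment is identical and blinded until the arms diverge, so these comparisons keep their randomised basis. AE start dates are already needed for the TEAE definition. End dates are assumed to be on the CRF, since Protocol 8.4.3 requires follow-up to resolution or stabilisation. No new visits are needed. The cost is a few more table shells and wide intervals at about 50 per arm.
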